The Baseline visit will occur in 14 days (+/- 7 days) from Screening. Participants will be instructed to remain fasting for 12 hours prior to the study day. This visit could take up to 3 hours. The study measures will be conducted by the IRB-approved study team who are all blinded to treatment allocation. The participants will first get a fasting blood draw at VAPORHCS. All study subjects will be provided breakfast after their fasting lab draw has been done. A fasting glucose level will be measured. Subjects will proceed with the following study measures: review and completion of questionnaires, medication inventory, physical performance tests, and whole body DXA. For those subjects who signed the consent indicating their interest in participating in the muscle biopsy substudy and are eligible, they will be scheduled for a Baseline muscle biopsy visit within 14 days of their

baseline visit.

Because adults with IFG have a higher risk of developing type 2 diabetes, all study participants will receive guidelines for diet and lifestyle modification consistent with the goals of the Diabetes Prevention Program at baseline and yearly visits.⁷² These include intake of < 25% of calories as fat and engaging in ≥ 150 minutes of physical activity weekly.

Baseline Muscle Biopsy Visit (if in substudy)

Participants enrolled in the muscle biopsy substudy will receive a telephone call within 3 days prior to their biopsy visits to remind them to fast for 12 hours prior to the visit, to remind them to abstain from vigorous physical activity, and to ensure they are not on anticoagulant or antiplatelet medications within 7 days from the biopsy visit with the exception of aspirin or other anti-inflammatory medications which cannot be taken within 3 days of the biopsy visit.

This visit will occur within 14 days from Baseline, and it could take up to 3 hours. It will be completed at OHSU. Eligibility criteria for the muscle biopsy will again be reviewed, and if there are no contraindications, the participant will undergo muscle biopsy. Participants will be given breakfast after muscle biopsy has been obtained.

Phone calls between visits

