At 3 and 9 month time points between annual visits, telephone surveying of medication compliance will be obtained. Any adverse events (AE) will be reviewed. A 24-hour phone number will be provided to participants to call in the event of any adverse outcome between these contact points. Additional phone calls may be made if subjects are found to be non-compliant.

All study participants will receive a telephone call to remind them to fast for 12 hours prior to their study visit.

Participants enrolled in the muscle biopsy substudy will receive a telephone call within 3 days prior to their biopsy visits to remind them to fast for 12 hours prior to the visit, to remind them to abstain from vigorous physical activity, and to ensure they are not on anticoagulant or antiplatelet medications within 7 days from the biopsy visit.

Half-Yearly Visits (6 months; Year 1 +6 months; Year 2 +6 months)

Half-yearly visits will occur at 6 Months, Year 1 + 6 Months, and Year 2 + 6 Months. All subjects will go to VAPORHCS for these visits. For those in the substudy, only for the 6 Month visit, they will also go to OHSU after labwork is drawn at VAPORHCS.

This visit could take up to 2 hours for participants (3 hours for participants in the muscle biopsy substudy at the 6 Month visit). At each half-yearly visit, all participants will have fasting labwork drawn, and have questionnaires reviewed and completed. Subjects >80 years old will get labs checked for creatinine and eGFR. Participants in the muscle biopsy substudy will undergo muscle biopsy if their morning STAT labs demonstrate platelet, INR, and aPTT levels in the normal range. Participants will be given breakfast after fasting lab work/muscle biopsy has been obtained.

Annual Visits (Years 1, 2, and 3)

These annual visits could take up to 3 hours. The participants will first get a fasting blood draw. They will then be given breakfast before proceeding with the following study measures: review and completion of questionnaires, medication inventory, physical performance tests, and whole body DXA.

Study Drug

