Imaging (DXA): DXAs will occur at OHSU. At Baseline and the annual visits, whole body scans will be taken with a Hologic QDR 4500W DXA scanner by a certified DXA operator to determine total body lean mass and appendicular lean mass (kilograms), as previously described.^{59, 60} Standard Hologic procedures will be used to define regions on the whole body DXA scans using cut lines. The arms will be delineated by a cut line drawn between the head of the humerus and the scapula at the glenoid fossa and the leg will be delineated by a cut line drawn across the midpoint of the femoral neck. Appendicular lean mass will be calculated as the sum of lean mass in the arms and legs. Hologic whole-body QC phantoms will be scanned daily to monitor longitudinal changes so that correction factors can be applied to measurements to adjust for longitudinal drift.

Muscle Biopsy studies (for those in the substudy): Subjects are asked to participate in the muscle biopsy studies based on their platelet and INR results. There will be 32 subjects in the substudy. Subjects will not enroll in the muscle biopsy studies or have a second muscle biopsy if they take medications that increase bleeding risk, have an allergy to lidocaine, or have platelet count < 150 billion/L, INR > 1.2, or aPTT > 36 seconds.

At the Baseline Muscle Biopsy visit and 6 month visit, fasting muscle biopsy samples will be obtained at OHSU by a physician or certified nurse practitioner from the vastus lateralis muscle, 15 cm above the patella using the modified Bergstrom technique, as described.^{36, 74-76} Using a 2% lidocaine for anesthetic, a small, ¹/₄ incision will be made in the skin and fascia to place a 5 mm Bergstrom biopsy needle while suction is applied through the 140 cc syringe, obtaining approximately 150-200 mg of muscle. The incision will be closed with sterile adhesive strips, and a pressure bandage will be applied for a period of 24 hours. This procedure takes approximately 15 minutes, is a relatively painless, and well-tolerated in older adults. Subjects will be instructed not to perform physical exercise 48 hours prior to the muscle biopsy procedure to help prevent acute effects of exercise on intramyocellular lipids (IMCL) (7:8). They will also be given discharge instructions after the procedure for precautions to follow to prevent complications.

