Muscle biopsy: The exclusion of participants on warfarin, clopidogrel, Aggrenox, ticlopidine, dabigatran or anagrelide will minimize serious bleeding with the procedure. We will also ensure that participants are not on these medications within a week of their second muscle biopsy. Furthermore, participants will have screening of INR, aPTT and platelets and will not be enrolled in the muscle biopsy substudy if there is any abnormality in clotting function to avoid serious bleeding. They will also have reassessment of these indices prior to the second

biopsy and will not undergo the second biopsy unless these labs are normal. Local anesthesia with 2% lidocaine will be used to reduce pain associated with the muscle biopsy. To ensure safety with the anesthetic, no participants with an allergy to lidocaine will be enrolled. To minimize the risk of infection from muscle biopsy, the procedure will be performed using sterile techniques. Appropriate pressure, hemostasis and use of an elastic wrap and ice bag after the biopsy will decrease the risk of bruising and aid in an anesthetic effect. Participants will be given instructions on care of the biopsy incision site to prevent bleeding and infection after the procedure.

DXA scans: The radiation exposure from one whole body DXA scan is 3.6 (4.6) μ Sv of radiation which is less than the accumulated daily background radiation dose to the whole body.³ Therefore even the amount of radiation from four DXA scans is nominal and should not raise the risk for adverse health effects.

Blood collection: A sterile technique will be used prior to venipuncture or intravenous access and pressure will be applied for appropriate hemostasis after withdrawal of the needle/catheter.

Physical Performance: To prevent harm from falls during the exam, neuromuscular tests will be administered by two staff members if the participant has a history of falling or is so frail that a fall might occur.

Protection Against Risk of Breach of Confidentiality

Subject confidentiality will be maintained in accordance with HIPAA regulations. The recruitment database will be protected by current network security in place in the VAPORHCS and all data collected prior to consent will be stored at VAPORHCS. After consent is signed, data will be maintained in the OCTRI/OHSU REDCap database. In addition, the database will be password protected, and only project personnel approved by [name] will be given access to them.

Potential Benefits of Research

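### The pre-biopsy call comes too late to secure the 7-day medication window it is meant to ensure, and its two descriptions differ on aspirin

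*Combined protocol and SAP*

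**What the plan says.** The call is described twice, under Baseline Muscle Biopsy Visit and again under Phone calls between visits. Both places say that substudy participants "will receive a telephone call within 3 days prior to their biopsy visits to remind them to fast". Both add that the call serves "to ensure they are not on anticoagulant or antiplatelet medications within 7 days from the biopsy visit". Both refer to biopsy visits in the plural, so the call precedes the baseline and the 6-month biopsy.

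The two descriptions then differ. The Baseline Muscle Biopsy Visit section continues "with the exception of aspirin or other anti-inflammatory medications which cannot be taken within 3 days of the biopsy visit". The Phone calls section stops at the 7-day rule and names neither aspirin nor anti-inflammatory drugs.

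Three other sections bear on the point:

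- Prohibited Medications gives the substudy a list of named bleeding-risk drugs, and the substudy exclusion criteria refer to that list. Plain aspirin and anti-inflammatory drugs are not on it.
- Muscle Biopsy studies, under Study Procedures, says: "Subjects will not enroll in the muscle biopsy studies or have a second muscle biopsy if they take medications that increase bleeding risk".
- Protection Against Risks of Study Procedures repeats the named drugs ("The exclusion of participants on warfarin, clopidogrel, Aggrenox, ticlopidine, dabigatran or anagrelide will minimize serious bleeding with the procedure") and adds: "We will also ensure that participants are not on these medications within a week of their second muscle biopsy".

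**The concern.** The call is given the task of ensuring a drug-free period that began before the call is made. Someone who may enrol while taking a drug subject to a window has to be told to stop before that window opens, and a call in the last three days cannot do this for a 7-day window. Staff who work from the Phone calls section alone would also never see the 3-day provision for aspirin and anti-inflammatory drugs.

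At stake are safety at the biopsy and the completeness of the histology data. When the call finds use, the biopsy is done inside the protocol's own window, postponed or lost. The documents do not say which should happen when the call itself finds use. A lost second biopsy removes one of 16 planned pairs in an arm.

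**Working it through.** The plan states no figure to reproduce. The check is a day count and a comparison of sections.

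**Inputs.** Call at most 3 days before the biopsy (both descriptions of the call). Windows of 7 days (both descriptions) and 3 days (Baseline Muscle Biopsy Visit only). Baseline biopsy within 14 days of the Baseline visit; 6-month visit window of ±7 days (footnotes to the Schedule of Study Procedures). Substudy of 32 participants, 16 per group, with two biopsies each (Muscle Biopsy studies; Sample Size and Power).

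**Step 1: days of the window already gone at the call.** Elapsed days = window length − days from call to biopsy.

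| Call made | 7-day window | 3-day window |
|---|---|---|
| 3 days before | 7 − 3 = 4 | 3 − 3 = 0 |
| 2 days before | 7 − 2 = 5 | 3 − 2 = 1 |
| 1 day before | 7 − 1 = 6 | 3 − 1 = 2 |

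No permitted call day reaches the start of the 7-day window. Only the earliest permitted day reaches the start of the 3-day window.

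**Step 2: who depends on the call for a timely instruction.**

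- *Listed drugs.* Users are excluded from the substudy, so the call only has to confirm that nothing has changed.
- *Aspirin and anti-inflammatory drugs.* They are not listed, so users may enrol, yet one section bars use in the last 3 days. These participants need to be told in advance.
- *Anticoagulants or antiplatelets outside the list.* The call covers the whole class, while the exclusion criteria point to the list. Users are in the same position, with a 7-day window.

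**Step 3: is an earlier instruction described?** Medications are recorded at Screening, inventoried at Baseline and recorded again at 6 months, but these steps are described as recording, not as instructing anyone to stop. The eligibility review at the baseline biopsy visit ("Eligibility criteria for the muscle biopsy will again be reviewed, and if there are no contraindications, the participant will undergo muscle biopsy") is later than the call. The same-morning platelet count, INR and aPTT at 6 months are laboratory values, not a record of drug use. The 3-month telephone contact covers study-drug compliance and adverse events. No earlier contact is described as dealing with these windows.

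**Step 4: what postponement would take.** Suppose a drug under the 7-day window is last taken on the day of the call and the full window is then observed. The biopsy moves by 7 − 3 = 4 days (call 3 days before) to 7 − 1 = 6 days (call 1 day before). A baseline biopsy planned after day 14 − 4 = 10, or after day 14 − 6 = 8, would then miss its 14-day limit. A 6-month visit planned for its target date would use 4 to 6 of the 7 days allowed after it. Under the 3-day window the move is 0 to 2 days.

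**Step 5: upper limit on scope.** 32 × 2 = 64 biopsies. One lost pair is 1/16 = 6.25% of an arm.

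**The case against.** The strongest reply is that the call verifies and was never meant to start a stopping period. The named drugs are prohibited in the substudy, and a late check of people already screened is sensible. This stands for the listed drugs. It does not cover aspirin, anti-inflammatory drugs or unlisted members of the class, whose users may enrol.

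A reader might infer that the call is the only medication check. It is not: medication history and exclusions are reviewed at Screening, an inventory is taken at Baseline, eligibility is reviewed again at the baseline biopsy visit, concurrent medications are recorded at 6 months, and there is a separate one-week commitment for the second biopsy. What can be said is narrower: the call is the only contact before the biopsy day that is described as addressing these windows.

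A reader might also infer that the exercise instruction comes too late and adds noise to the intramyocellular lipid measure. The documents do not support this. The protocol says "Subjects will be instructed not to perform physical exercise 48 hours prior to the muscle biopsy procedure" without saying when or how, and the exercise item in the call is worded as a reminder, which presupposes an earlier instruction.

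Three further replies have some force. The enrolment list and the pre-procedure check serve different purposes, so their different scope is not in itself a contradiction; it matters because it determines who can enrol and still need an instruction. Postponement is often possible, as Step 4 shows, but the plan does not provide for it when the call finds use. Finally, the consent pages are not available here and the full content of the mailed reminder letters is not given, so an earlier instruction may exist. The point is that the protocol does not describe one.

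**Conclusion.** The concern holds in a limited form. The call cannot secure a 7-day window, because at least 4 of the 7 days have passed when it is made. For aspirin and other anti-inflammatory drugs it meets the 3-day window only if made on the first permitted day. The two descriptions of the call also need to be reconciled.

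A reader might take the documents to state a 7-day aspirin window in one place and a 3-day window in another. They do not. The Phone calls section omits the exception, and 7 days follows only by implication, because the other section words aspirin as an exception to the 7-day rule. For other anti-inflammatory drugs the Phone calls section gives no clear window.

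The number of biopsies affected cannot be derived from the documents. The firm figure is an upper limit of 64 biopsies. If 20% to 50% of participants used aspirin or an anti-inflammatory drug (an assumption), 64 × 0.20 ≈ 13 to 64 × 0.50 = 32 biopsies would be in users. How many calls came too late would still depend on the window retained and on when calls are made, which is unknown.

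The consequence is confined to the substudy: a biopsy inside the protocol's own window, or a postponed or lost pair out of 16 per arm. The primary analysis and its sample size are not affected. The conclusion assumes that no earlier instruction is given in material not available here.

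**What to change.** 1. Reconcile Prohibited Medications, Baseline Muscle Biopsy Visit, Phone calls between visits, Muscle Biopsy studies and Protection Against Risks of Study Procedures on three matters: the length of the window, the drugs it covers, and the status of aspirin and other anti-inflammatory drugs. Which window applies is for the investigator to decide.
2. Give the medication instruction before the longest window retained, for example at the Baseline visit and in the reminder letter already mailed before the 6-month visit. Keep the 3-day call as a fasting reminder and re-check.
3. State what follows when the call finds use.

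The cost is a line in an existing letter and a short item at the Baseline visit. The small downside is less freedom in scheduling the baseline biopsy. If the instruction is given at Baseline and a 7-day window is kept, the biopsy could fall no earlier than about day 7 of the 14 days allowed; with a 3-day window, no earlier than about day 3.

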Older adults with impaired fasting glucose (IFG) will be randomized to into a double-blinded, placebo-controlled intervention study with metformin. This clinical trial has the primary outcome of change in appendicular lean mass and physical performance assessed between baseline and year 3 based on our prior observational findings above and Power calculations below. The secondary outcome of change in muscle histology over 6 months using muscle biopsies is planned in a substudy of participants given previous studies that show significant biological effects on muscle with metformin treatment during this time interval.^{32, 61}

Study Population

Inclusion criteria: 120 randomized, sedentary, weight-stable, ambulatory men and women 65 years or older with pre-diabetes identified with IFG (100 mg/dL \leq fasting glucose<126 mg/dL) on no diabetes medications. Participants must demonstrate that they are able to ambulate 400 meters without assistance. Participants must be able to fast for 12 hours prior to blood draw.

Subjects who meet the above inclusion criteria and meet the additional exclusion criteria for the Muscle Biopsy Substudy listed below will be considered for enrollment (32 subjects) in the muscle biopsy substudy.

Exclusion criteria: Participants will be excluded if they plan to move away from the Portland metropolitan area during the 3 year study time frame. Participants with conditions that are relative contraindications to metformin or affect muscle mass or performance measurements will be excluded as outlined below. Specific criteria are delineated below.

Exclusion Criteria

- 1. Chronic medical conditions affecting muscle mass or function
 - a. Active non-skin cancer
 - b. Hypogonadism
- 2. Medications affecting muscle mass or function See section "Prohibited Medications."
- 3. Lifestyle factors affecting muscle
 - a. Intentional/unintentional weight loss
 - b. Vigorous regular exercise
- 4. Contraindications to metformin
 - a. Renal dysfunction defined as creatinine $\geq 1.5~mg/dL$ for men or $\geq 1.4~mg/dL$ for women or eGFR< 60 mL/min
 - b. Liver dysfunction defined as ALT > 48 U/L, AST > 41 U/L
 - c. B12 deficiency defined as B12 level < 180 pg/mL
 - d. Congestive heart failure
 - e. Known hypersensitivity to metformin
 - f. Excessive alcohol intake (average of ≥ 2 alcoholic beverages/day over a month)
 - g. Serious medical condition in the opinion of the investigator

Additional Exclusion Criteria for Muscle Biopsy Substudy

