Initial contact with potential subjects will occur in clinic, by phone or by mail. If in clinic, their provider will approach them first to see if they are interested in the study and ask if they agree to be contacted by study personnel. If the patient agrees, they can initiate contact with the study team by phone or have the study coordinator speak to them in clinic or call them later. If initial contact is by phone, potential subjects can contact the study coordinator directly using information on the advertising flyers. If initial contact is by mail, potential subjects will receive a recruitment letter indicating the option to opt out by returning an included letter indicating the wish to not be contacted again. The letter will state that if a response is not received within two weeks, potential subjects may be contacted by phone. Included with this mailing will be an approved informational letter from the Chief of Primary Care.

During the screening telephone call, a study coordinator will discuss the inclusion and exclusion criteria and provide further details on the study. If participants are interested and are potentially eligible, a Screening visit will be scheduled.

Study design

The proposed study duration of 3 years has been selected based on our prior observational findings over 3.5 years.²⁵ Eligible participants will have an initial Baseline visit, followed by randomization to placebo or metformin (Fig. 7). Between visits, telephone surveying of medication compliance will be obtained and any AEs reviewed. Participants will be seen every 6 months, and have annual study visits for measurements of muscle mass and performance. A substudy of participants will also include muscle biopsies at 2 visits; within 14 days from baseline and at the 6 month visit.

9

Primary outcome measures

To test the primary hypothesis that metformin-treated participants will have a slower decline in muscle mass and physical performance than those on placebo, we will be measuring total and appendicular lean mass using dual x-ray absorptiometry and assessing physical performance with the short physical performance battery (SPPB), grip strength and a 400 meter walk. Our preliminary findings suggest that there should be attenuation in the loss in appendicular lean mass and gait speed, and additional performance measures will be explored.

Secondary outcome measures

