Instances where the study drug is discontinued include the following: development of a contraindication to metformin as described under the section for exclusion criteria; development of lactic acidosis; diagnosis of diabetes; hospitalization; 48 hours prior to procedures or scans that require contrast medium; or development of B12 deficiency. For those who are hospitalized or receive contrast medium, efforts will be made to recheck kidney function within 48 hours after discharge/procedure and the study drug will be restarted if there is no evidence of renal dysfunction. For tests or procedures that require fasting, study drug will be stopped 24 hours prior to test or procedure, and study drug can be resumed after the participant is allowed to eat again. Compliance to study drug will be tracked and accounted for in analyses.

Study Procedures

All study procedures are research-related.

Exam: Exams for annual visits will occur at OHSU after fasting labwork has been drawn at VAPORHCS. At Screening, baseline and yearly exams, height will be measured in meters using a wall-mounted Harpenden stadiometer, body weight will be measured in kilograms using a balance beam scale, waist and hip circumference measured with a tape measure, and measurements of pulse and blood pressure will be taken.

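### Participants arrive fasting but eat before the DXA, and the meal is not standardized, which adds small, avoidable noise to total lean mass

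*Combined protocol and SAP*

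**What the plan says.** Fasting on arrival is part of the plan: "All study participants will receive a telephone call to remind them to fast for 12 hours prior to their study visit" (Phone calls between visits). At Years 1, 2 and 3 blood is drawn first, and then "They will then be given breakfast before proceeding with the following study measures"; the list that follows ends with the whole body DXA (Annual Visits). For Baseline the protocol states "All study subjects will be provided breakfast after their fasting lab draw has been done" and only afterwards lists the measures, again including DXA (Baseline Visit). That order is read from the sequence of the text and is not stated as a rule.

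Under Primary outcome measures, "we will be measuring total and appendicular lean mass using dual x-ray absorptiometry". The Overview is narrower: "This clinical trial has the primary outcome of change in appendicular lean mass and physical performance assessed between baseline and year 3". The Imaging (DXA) section defines the narrower measure: "Appendicular lean mass will be calculated as the sum of lean mass in the arms and legs".

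The Meals section says which unit supplies breakfast. It gives no content, weight, fluid volume or timing, and the Imaging (DXA) section sets no rule on time since eating.

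Two sites are involved. "DXAs will occur at OHSU" (Imaging), and "Exams for annual visits will occur at OHSU after fasting labwork has been drawn at VAPORHCS" (Exam).

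**The concern.** Whole body DXA separates soft tissue into fat and lean. Food and drink in the gut fall largely into the lean compartment of the trunk. This is a general property of the measurement and is not discussed in the protocol. A scan after breakfast therefore counts part of the breakfast as lean mass.

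The participants are already fasted when they arrive, so the chosen order gives up a fasted scan that is available. If the meal, or the interval from meal to scan, differs between Baseline and a later visit, the difference enters that person's change in total lean mass. The daily phantom scans correct for scanner drift, but they cannot correct for what a participant ate. At stake is some precision in one of the two DXA measures listed as primary.

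**Working it through.** **The plan's own figure.** Sample Size and Power gives a 2.2% difference in percentage change in appendicular lean mass, SD 4%, two-sided α of 0.05, 80% power and an unpaired t-test, leading to 53 per group (106 in total). The noncentral t solution for a standardized difference of 2.2/4 = 0.55 is 52.87, so 53 per group; power at 53 is 80.1%. The figure reproduces. It concerns appendicular lean mass, which leaves out the trunk, so the meal does not change it.

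**Total lean mass.** The documents give no effect size, SD or power for this measure, so the rest is illustrative. Assumptions:

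- between-visit SD of the ingested mass present at the scan, s = 0.2 to 0.4 kg (not in the documents);
- total lean mass, L = 50 to 55 kg (not in the documents);
- SD of change without meal noise, 4% (borrowed from appendicular lean mass).

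**What cancels.** Write the measured value at a visit as true lean mass + m + e, where m is the average meal and e its deviation, with SD s. Baseline and follow-up are both fed, so m drops out of the change. What remains is the difference of two deviations, with variance 2s².

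**Added variance.**

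- s = 0.2 kg: 2 × 0.2² = 0.08 kg²
- s = 0.4 kg: 2 × 0.4² = 0.32 kg²

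**Variance of change without the meal.**

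- L = 50 kg: (0.04 × 50)² = 4.00 kg²
- L = 55 kg: (0.04 × 55)² = 4.84 kg²

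**Relative increase.**

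- Smallest: 0.08/4.84 = 1.7% in variance; √1.017 = 1.008, so 0.8% in SD (4.00% becomes 4.03%).
- Largest: 0.32/4.00 = 8.0% in variance; √1.08 = 1.039, so 3.9% in SD (4.00% becomes 4.16%).

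**In terms of power.** If the 2.2% difference is also borrowed, the same t-test at 53 per group has 80.1% power without meal noise, 79.5% at the smallest increase and 77.0% at the largest. The loss is about 0.6 to 3.1 percentage points.

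**Wider assumptions.** With L = 45 to 65 kg and s up to 0.3 kg, power stays at 77.9% or above, a loss of roughly 0 to 2 points. At the extreme corner (s = 0.5 kg, L = 45 kg) the SD becomes 4.30% and power 74.2%, a loss of about 6 points.

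**The case against.** The strongest reply is that the point misses the measure that drives the trial. The Overview names appendicular lean mass and physical performance, the sample size rests on appendicular lean mass, and arms plus legs exclude the gut. That stands, and it confines the point to total lean mass.

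Second, the protocol does not say that breakfast varies. The study supplies it, and a constant meal cancels. That also stands: variability is inferred from silence. But nothing in the documents limits it, neither in content nor in time to scan.

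Third, scanning first is not free. Blood is drawn at VAPORHCS and the scanner is at OHSU, so people aged 65 or older would fast through a transfer and a scan. This is a real cost, though a modest one: at the 6-month visit, biopsy participants already have labs at VAPORHCS, move to OHSU and eat only after the procedure.

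A reader might go further and infer a bias against metformin: gastrointestinal symptoms could make treated participants eat less, so that they appear to lose lean mass. The documents do not support this. Risks of Metformin Use ties these symptoms to starting the drug, the section on protection against those risks calls them self-limiting and links continued use with stable weight, and the first on-treatment DXA is at Year 1. No figure for reduced intake is given. Nor should any such shift in total lean mass be set against the 0.34 kg difference between metformin users and normoglycemic men (0.75 − 0.41) in the preliminary data, because that difference is appendicular.

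**Conclusion.** The point holds as a minor matter of measurement precision. The visit order lets meal-to-meal differences into change in total lean mass, and the protocol has no control for them. On the assumed inputs this adds about 2-8% to the variance of change, or roughly 1-4% to its SD. The size depends on a meal SD and a total lean mass that the documents do not give, and on an SD borrowed from appendicular lean mass.

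No stated figure changes, and the appendicular lean mass outcome is largely unaffected. Both arms are blinded and are fed in the same way at Baseline and follow-up, so the expected effect is noise; a directional error is not shown. Scanning before breakfast is a cheap improvement rather than a necessary correction.

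**What to change.** In Baseline Visit and Annual Visits, state the order as fasting blood, whole body DXA, breakfast, then questionnaires and performance tests, and apply it at Baseline and Years 1, 2 and 3.

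Add a transition rule. Any participant whose Baseline scan was taken after breakfast should keep the fed order throughout, with the breakfast and the time from meal to scan standardized and recorded. Otherwise a fed Baseline would be compared with a fasted follow-up, and the constant part of the meal, which now cancels, would appear as lost lean mass. The documents do not say how many participants this concerns. The Labs section applies a recently changed eGFR limit to continuation of study drug, which suggests that some may already be on treatment.

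The cost is a later breakfast for older adults, by the transfer to OHSU and the length of one scan. No extra procedure is needed.
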